10.1.2 Analysis of secondary endpoints

10.1.2.1. Safety

Patients will be assessed for toxicities at each clinical evaluation. Toxicities will be graded according to CTC v4.0 standardized grading scales. The incidence of grade 3-5 toxicities will be reported. Patients will be assessed for toxicity as long as they are taking olaparib, and patients will continue to be followed if olaparib is discontinued for toxicity until the toxicities improve to grade 1 or resolve.

Toxicities will be reported as a tabulated table by type and grade.

If >1 participant is diagnosed with MDS or AML during the trial, then the trial will be stopped for concerns about safety.

10.1.2.2. PSA progression-free survival (PFS)

Patients in this trial can remain on olaparib as long as they are not experiencing toxicity requiring cessation of drug and until their PSA reaches a value that is double that of the value on enrollment in the study. However, for purposes of reporting this secondary endpoint, a standard definition of PSA progression per PCWG3 will be used. PSA PFS will be defined as an increase in 25% over a nadir value, confirmed by a follow-up PSA at least 4 weeks apart. If patients are removed from study prior to PSA progression, then they will be censored at that time.

We will use the Kaplan-Meier method to estimate the median PSA PFS.

10.1.2.3. Time to PSA doubling from baseline:

Patients in this trial can remain on olaparib as long as they are not experiencing toxicity requiring cessation of drug, not experiencing clinical progression of disease, and until their PSA reaches a value that is double that of the value on enrollment in the study. A confirmatory PSA at least 4 weeks later is required; and the time point used for calculation of this endpoint will be the first of those values.

We will use the Kaplan-Meier method to estimate the median time to PSA doubling.

10.1.2.4. Undetectable PSA:

A durable undetectable PSA endpoint will be defined as a patient on study with olaparib who achieves a PSA < 0.1, which is confirmed with a repeat measurement at least 12 weeks later. This endpoint will represent a durable complete metabolic response to olaparib. This endpoint can only be achieved while on therapy with olaparib, although the confirmatory values after initially achieving undetectable PSA may be measured while off therapy for olaparib.

The durable complete PSA response rate will be estimated as number of patients achieving a durable complete PSA response divided by enrolled patients with an exact 95% confidence interval.

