Duration of Intervention and Evaluation: Patients will be treated until toxicity requiring cessation, doubling of PSA from baseline, confirmed by a second measurement at least 4 weeks apart, or clinical/radiographic progression, defined as development of symptoms related to prostate cancer or metastatic disease on CT or NM Bone Scan. Patients will be monitored monthly while on therapy. After completion of study treatments, they will be monitored for at least 1 month after any grade 2 or higher toxicities return to grade 1 or resolve.

Statistical Methods:

(a) Definition of primary endpoint: The primary endpoint of this study is PSA₅₀ response, defined as a decrease in the PSA to 50% less than the baseline PSA upon enrollment in the trial. The decrease must be confirmed by a second measurement at least 4 weeks apart. For purposes of meeting the primary endpoint, patients will be considered to have done so if they have a PSA₅₀ response only while on therapy with olaparib. PSA values will be measured monthly during the trial. All patients who are administered at least one dose of olaparib will be considered evaluable for the primary endpoint. If patients do not have follow-up PSAs after initiation olaparib therapy due to stopping therapy for toxicity or withdrawing consent, then they will be considered non-responders. If the biomarker-enriched stage is necessary, that cohort will be evaluated separately from the initial stage(s) of the trial.

(b) Definition of secondary endpoints:

- i. Safety: Patients will be assessed for toxicities at each clinical evaluation. Toxicities will be graded according to CTC v4.0 standardized grading scales. The incidence of grade 3-5 toxicities will be reported. Patients will be assessed for toxicity as long as they are taking olaparib, for at least 30 days after stopping, and will continue to be followed if olaparib is discontinued for toxicity until the toxicities improve to grade 1 or resolve.

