Physical exam	X	X	X	X	X	X
Vital signs (P, BP, RR, T)	X	X	X	X	X	X
Height	X					
Weight	X	X	X	X	X	X
ECOG Performance status	X		X	X	X	X
Toxicity assessment	X		X	X	X	X
Concomitant meds	X	X	X	X	X	X
Histologic confirmation and Tissue/DNA studies	X ^f					
Radiologic tests ^b	X				X ^b	X ^b
Laboratory tests ^c	X	X ^g	X	X	X	X
Olaparib			X	X	X	
Adverse events			X	X	X	X

Abbreviations: CBC, complete blood count; CT, computerized tomography; MRI, magnetic resonance imaging; PSA, prostate-specific antigen

^a Informed consent and radiologic assessments should be obtained within 4 weeks of study start date.

^b Radiographic evaluations (CT A/P and NM Bone Scan every 6 months while enrolled in the study). They are needed within 28 days of screening; if previously performed then they are to be performed at screening. CT A/P and NM Bone Scan are to be performed at off-treatment visit if they have not been performed in the prior 3 months.

^c CBC w/diff, Complete Metabolic Panel, PSA at each visit. Testosterone, PT/INR, PTT, and Urinalysis at screening visit only. Note: Patients with creatinine clearance between 51- 80 mL/min either at trial enrolment or during the course of the trial should be monitored every 2 weeks for laboratory assessment and toxicity evaluation.

^d For Cycle 1 and Cycle 2, CBCs will be repeated weekly.

^e Subjects will be followed after completion of olaparib therapy monthly until toxicities resolve to grade 0-1.

^f Tissue from prostatectomy sent to Foundation Medicine and GenomeDx

^g C1D1 routine labs (CBC w/diff, Comprehensive Metabolic Panel, PSA) are only required if >7 days since screening labs.

^h In order to minimize the need for research-only in-person visits, telemedicine visits may be substituted for inperson clinical trial visits or portions of clinical trial visits where determined to be appropriate and where determined by the investigator not to increase the participants risks. Prior to initiating telemedicine for study visits the study team will explain to the participant, what a telemedicine visit entails and confirm that the study participant is in agreement and able to proceed with this method. Telemedicine acknowledgement will be obtained in accordance with the Guidance for Use of Telemedicine in

Olaparib in Biochemically Recurrent Prostate Cancer
Johns Hopkins

Protocol No. IRB00114635

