5.6 End of Treatment/Treatment Discontinuation Visit (28 days after last dose ±3 days)

- conduct physical exam (including vital signs, height/weight)
- perform laboratory tests: Complete blood count w/Diff, PSA, Comprehensive metabolic panel
- assess performance status (ECOG). (Appendix A)
- review concurrent medications
- assess AEs
- if patient is discontinuing participation in study, perform radiographic tests: CT A/P and NM Bone Scan (if these have not been performed in the prior 3 months)

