5.7 Follow-up (At least every 28 days while active AEs)

Patients will be followed every 28 days beyond the end of treatment visit if they have withdrawn from study because of AEs. Patients withdrawn from the study because of AEs will be followed until the adverse event has either resolved or stabilized. Reasons for premature withdrawal should be determined and noted. To be performed at each visit will be:

- conduct physical exam (including vital signs, height/weight)
- perform laboratory tests (CBC w/diff, Comprehensive metabolic panel) only as indicated by AEs requiring follow-up
- assess performance status (ECOG). (Appendix A)
- review concurrent medications
- reassess AEs.

- When patient will discontinuing participation in study, perform radiographic tests: CT A/P and NM Bone Scan (if these have not been performed in the prior 3 months)

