6.4 Removing Patients from the Protocol

Patients may be discontinued from investigational product (IP) in the following situations:

- Patient decision. The patient is at any time free to discontinue treatment, without prejudice to further treatment

- Severe non-compliance with the study protocol
- Bone marrow findings consistent with myelodysplastic syndrome (MDS)/acute myeloid leukaemia (AML)
- Potential Hy's Law cases (AST or ALT $\geq 3 \times$ ULN and TBL $\geq 2 \times$ ULN with no other reason)
- Disease progression by symptomatic or radiographic assessment
- PSA doubling from baseline value, confirmed by a second value at least 4 weeks apart, with a minimum time since initiation of therapy of 12 weeks.
- Intercurrent illness that prevents further administration of treatment
- Unacceptable adverse events that may or may not be directly related to treatment but that, in the judgment of the treating physician, makes it dangerous for the patient to be retreated.
- Adverse events requiring cessation of olaparib, with inability to restart therapy within 14 days.
- General or specific changes in the patient's condition that render the patient unacceptable for further treatment, in the judgment of the investigator

Because an excessive rate of withdrawals can render the study uninterpretable, unnecessary withdrawal of patients should be avoided. When a patient discontinues treatment early, the investigator should make every effort to contact the patient and to perform a final evaluation. The reasons for withdrawal should be recorded.

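### Does PSA progression-free survival need redefining because men who stop for metastasis or symptoms may be censored and death is not mentioned?

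*Combined protocol and SAP*

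**What the plan says.** Four places define the endpoint: the synopsis list of secondary endpoints, synopsis Statistical Methods (b) ii, section 8.1.2.2 and section 10.1.2.2. In all four the only event is a PSA rise of 25%, confirmed at least 4 weeks later. All but the synopsis list state that the rise is measured from nadir. Synopsis (b) ii and section 10.1.2.2 share the censoring rule: "If patients are removed from study prior to PSA progression, then they will be censored at that time".

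The text bearing on removal is as follows.

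- Section 6.4 has a heading about removing patients from the protocol, but its list opens with "Patients may be discontinued from investigational product (IP) in the following situations". It includes "Disease progression by symptomatic or radiographic assessment".
- The synopsis (Duration of Intervention and Evaluation) also ends treatment for "clinical/radiographic progression, defined as development of symptoms related to prostate cancer or metastatic disease on CT or NM Bone Scan".
- Section 5.6 takes a PSA 28 days after the last dose. It treats leaving the study as a separate condition: "if patient is discontinuing participation in study, perform radiographic tests".
- For later visits, Table 2 footnote c has "CBC w/diff, Complete Metabolic Panel, PSA at each visit", while section 5.7 has "perform laboratory tests (CBC w/diff, Comprehensive metabolic panel) only as indicated by AEs requiring follow-up" and lists no PSA. Footnote e ties those visits to toxicity: "Subjects will be followed after completion of olaparib therapy monthly until toxicities resolve to grade 0-1".

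Death appears under safety reporting, not in this endpoint.

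**The concern.** An endpoint called progression-free survival would usually count radiographic progression and death as failures. Here a man whose scan shows metastasis before his PSA has risen 25% may be censored, as if he had simply been lost to view. Section 1.1.3 links a shorter PSA doubling time to earlier metastasis, so such censoring could be informative and push the Kaplan-Meier median upward.

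Because removal is not defined, one analyst might censor that man when olaparib stops, and another might keep him at risk until follow-up ends. At stake would be a reported median that depends on an unstated convention and is read as more than a PSA result.

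**Working it through.** The documents give no expected median, event count or censoring rate for this endpoint, so there is no stated figure to reproduce. The check has four steps.

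**1. Which men can be affected.** A man who stops for confirmed PSA doubling is never censored by the rule. His PSA is at least 100% above baseline, and nadir cannot exceed baseline, so he has already passed 25% over nadir. The question is confined to men who stop for scans, symptoms or other reasons, or who die, before a PSA event.

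**2. When scan-detected metastasis can move the median.** At the entry limit (doubling time 6 months), a 25% rise takes 6 × log2(1.25) = 1.93 months. The first on-study scan comes at six 28-day cycles (section 5.3.1), 168/30.4375 = 5.52 months, or at 6 months (Table 2). The median can move only if over half the men are free of PSA progression at that scan.

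- *Unselected alternative, response 0.3 (section 10).* Suppose every responder is free. Then (0.5 − 0.3)/0.7 = 28.6% of non-responders must also be free. With doubling times assumed uniform on 1.5 to 6 months, the 71.4th percentile is 1.5 + 0.714 × 4.5 = 4.71 months. PSA growth must slow by 5.52/(0.3219 × 4.71) = 3.6-fold, or 6/(0.3219 × 4.71) = 4.0-fold, where 0.3219 = log2(1.25).
- *Enriched alternative, response 0.6.* With no slowing in non-responders, 0.5/0.6 = 83% of responders must be free.

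**3. Size if that happens.** Assumptions: constant hazards; metastasis median 24 months (synopsis, Disease Background), counted from first dose; metastasis dated at the next scan (every 5.52 or 6 months); correlation 0.5 or 0.8 through a Gaussian copula; one million simulated men, two seeds. The last column assumes independence: S(t) = exp(−ln2·t/m) × exp(−(ln2/24)·s·floor(t/s)), where m is the PSA-progression median and s the scan interval.

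| PSA-progression median (months) | Overstatement if censored at drug stop, correlated | Drug-stop reading minus reading 28 days later, correlated | Median if metastasis counts as an event, independent |
|---|---|---|---|
| 4 | 0 | 0 | 4.0 |
| 6 | under 0.05 | under 0.05 | 5.5–6.0 |
| 9 | 0.2–0.3 | 0.1 or less | 6.8–6.9 |
| 12 | 0.5–0.7 | 0.16–0.23 | 9.0–9.2 |

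Under independence the first two differences are zero. With correlation, the composite median at 12 months is 10.8 to 11.8. Metastasis is found first in 0.2% to 8% of men at a 4-month median and in 9% to 28% at 12 months. If metastasis is also delayed (assumed median 48 months), the overstatement at 12 months falls to 0.1–0.3 month.

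**4. Why the two readings lie so close.** After drug stop, section 5.6 schedules one more PSA at 28 days, and later visits depend on adverse events. With no further PSA, a man kept nominally at risk is censored at his last value anyway. A rise first seen at that 28-day visit also needs a confirming value that is not routinely scheduled. The model counts such rises without confirmation, so column three is on the generous side.

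**Scale.** With all 50 men followed to an event, the standard error of a 12-month Kaplan-Meier median under a constant hazard is m/(ln2 × √n) = 12/(0.693 × 7.07) = 2.4 months.

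**The case for a change.** The strongest reply is that the gap exists whatever its size. Section 6.4 governs stopping the drug and is not linked to the censoring rule, and section 5.6 separates stopping from leaving. The drafters were explicit for the primary endpoint, where section 10.1.1 says how men without follow-up PSA count and that the confirming value may be off therapy; PSA PFS has no such statement. Metastasis-free survival does not fill the gap, since it is exploratory and runs from biochemical recurrence. The effect also grows where olaparib gives durable PSA control, which is when the median would attract most attention.

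Much of this stands as description. Removal is undefined, death is not addressed, Table 2 and section 5.7 disagree on follow-up PSA, and the synopsis list omits the nadir. Men with lasting adverse events could have further PSA values, so the two readings could differ more for them; that subset is not modelled. Symptomatic progression and death are not modelled either.

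What does not follow is that the analysis is wrong. Synopsis (b) ii names clinical progression as a reason to stop and then, in contrast, chooses a PSA-only event for reporting. The label begins with PSA, and no definition suggests a composite. The 9-month figure answers a different question, and it keeps an untreated metastasis rate while letting olaparib hold PSA for a year.

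**Conclusion.** No change to the plan follows. Read as written, the endpoint is a time to PSA progression, and the Kaplan-Meier median is a reasonable estimate of that. Renaming it or adding events is a choice between estimands on which statisticians differ.

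The undefined term is a gap that analysts fill sensibly: take section 6.4 as the list of removals, censor at the last PSA, and show the number censored by reason, including any deaths. The missing nadir in the synopsis list is a clerical slip, corrected by the other three definitions. The disagreement over follow-up PSA concerns visits held for adverse events.

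The choice of reading is worth nothing at a 4-month PSA-progression median and about 0.2 month at most at 12 months. Informative censoring adds at most about 0.7 month, at an assumed 12-month median with assumed correlation, against a standard error of at least 2.4 months. These sizes rest on constant hazards, the 24-month metastasis median taken from first dose, and the written visit schedule. Symptomatic progression and death before PSA progression remain unquantified because the documents give no rates. No test, sample size or stopping rule uses this endpoint.

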10.1.2 Analysis of exploratory endpoints

10.1.2.1. Biomarker positive and biomarker negative PSA₅₀ response calculations: All subjects in the trial will be considered either a responder or non-responder based upon the meeting of the primary endpoint based upon the definition above. For each patient, the DNA mutations present in the tumor will be identified through Foundation Medicine sequencing and/or through plasma cell-free DNA analysis. Patients with a deleterious mutation in the pre-specified gene list (ATM, BARD1, BRCA1, BRCA2, BRIP1, CDK12, CHEK1, CHEK2, FANCL, PALB2, PPP2R2A, RAD51B, RAD51C, RAD51D or other DNA repair genes) will be considered biomarker positive. For biomarker positive and biomarker negative subjects, we will calculate response rates with confidence intervals for hypothesis generation. Separate calculations for each testing modality will occur. If a biomarker selected population is accrued, then the response rate in the biomarker positive population will be reported as the primary analysis. If the trial proceeds with an unselected population only, then these calculations will be reported as exploratory endpoints.

10.1.2.2. Development of gene signature for response: based upon the responders and the DNA mutations identified through sequencing, a discovery of a biomarker set will take place by exploring which grouping of mutations are associated with response, using both descriptive analyses and random forest methods.

10.1.2.3. RNA expression profile signature positive and negative PSA₅₀ response calculations: Similarly to above, subjects will have tumor tested with RNA expression profiling and scored for likelihood for response to olaparib per the Decipher GRID platform (GenomeDx). For subjects considered to have a positive

RNA expression signature based upon a binary score assigned via the GenomeDx proprietary algorithm, a PSA_{50} response rate will be calculated. Similarly, a calculation will be performed for subjects considered to have a negative RNA expression signature.

10.1.2.4. PARP-1 and γ H2AX protein levels: Subjects will have prostatectomy samples analyzed for baseline PARP-1 and γ H2AX proteins, and scored for positivity by immunohistochemistry on scale of 0 (none) to 3 (intense staining), and the results will be associated with responses for both proteins, separately, using descriptive statistics and Fisher's Exact Tests.

10.1.2.5. Metastasis-free survival analysis: the median MFS will be estimated using the Kaplan-Meier method.

10.1.2.6. Time to next anti-cancer therapy analysis: similarly to MFS, this time to event analysis will be estimated using the Kaplan-Meier method.

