1.3.2 Rationale for conducting study

There are several pending trials are being conducted with olaparib for patients with metastatic CRPC, including olaparib as monotherapy (NCT01682772) and olaparib in combination with enzalutamide (NCT02500901). The FDA recently announced breakthrough designation for olaparib for metastatic CRPC, refractory to novel hormone

therapy and chemotherapy, with mutations in BRCA1, BRCA2, or ATM. While PARP inhibition is showing promise in these initial studies, reserving its use for end-stage patients may not be the optimal timing for olaparib therapy in some patients. PARP inhibition has not been tested in earlier disease states for prostate cancer.

Olaparib may be an ideal therapy for men with biochemically recurrent prostate cancer. PARP inhibition with olaparib in this earlier disease state may be more effective in hormone-sensitive prostate cancer (rather than in heavily pre-treated/resistant tumors), as tumor heterogeneity may be significantly lower. In addition, it is unknown whether genetic changes identified in prostatectomy specimens will be predictive of response to olaparib. PARP inhibition may also be active in ways beyond the DNA repair pathway for prostate cancer. This trial will attempt to test questions regarding the activity of olaparib in hormone-naïve prostate cancer and explore associations between responses with genetic mutations and expression profiles identified in the primary prostatectomy specimens.

In this trial, subjects will be enrolled with biochemically recurrent prostate cancer. Patients will be required to have undergone prior definitive radical prostatectomy with tissue available for analysis. Patients will also have required to have previously been treated with salvage radiation therapy, declined salvage radiation therapy, or were not candidates for salvage radiation. By requiring prior definitive therapy and attempted salvage therapy, the enrolled patients are those that are not felt to have known curative options remaining for their cancer.

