10. STATISTICAL CONSIDERATIONS

This study will enroll up to 50 subjects. The study design will employ a stepwise adaptive statistical plan, derived in part from Biankin *et al.* [27]. The design is adapted from a multi-stage design, with interim stopping rules to determine futility or need for enrichment of the study population.

The study will initiate with a two-stage design in an unselected population. The assumptions for the trial of the unselected population are: null hypothesis of 0.1 PSA response rate and alternative hypothesis of 0.3 for the unselected population. The first stage is 20 subjects. If ≤ 2 subjects respond in the first stage, then unselected population study is halted for futility and an assessment of DNA mutations present in the initial cohort will be undertaken. If less than 3 subjects with a known/suspected deleterious mutation in the following genes (ATM, BARD1, BRCA1, BRCA2, BRIP1, CDK12, CHEK1, CHEK2, FANCL, PALB2, PPP2R2A, RAD51B, RAD51C, RAD51D or other DNA repair genes) have been accrued in the first stage, then the trial will proceed with enrichment. If 3 or more subjects with known/suspected deleterious mutation in the genes of interest have been accrued, then the trial will proceed with enrichment, as long as the response rate in that subset of subjects is $\geq 20\%$. In the case that 3 or more subjects have been accrued, yet the response rate in that subset is $< 20\%$, then the trial is halted for futility.

However, if ≥ 3 subjects among the first 20 respond, then additional 10 unselected subjects are accrued. If ≥ 6 subjects respond out of 30 in the unselected population after the second stage, then the null hypothesis is rejected in the unselected population and broad efficacy will be concluded. The trial proceeds to complete accrual of 50 subjects in order to better estimate PSA response rate and strengthen data for correlative studies. If < 6 respond, then the null hypothesis is not rejected. Again, if less than 3 subjects with a known/suspected deleterious mutation in the following genes (ATM, BARD1, BRCA1, BRCA2, BRIP1, CDK12, CHEK1, CHEK2, FANCL, PALB2, PPP2R2A, RAD51B, RAD51C, RAD51D or other DNA repair genes) have been accrued in the first and second stage combined, then the trial will proceed with enrichment. If 3 or more subjects with those mutations have been accrued, then enrichment will again proceed as long as the response rate in that subset of subjects is $\geq 20\%$.

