10.2.2 Estimation of Power

Assuming that the response rates for all-comers is 0.3 and the response rate for the biomarker selected population is 0.6 (both alternative hypotheses), estimates for power were generated using the simulation. Two scenarios are presented: prevalence of biomarker positive subjects of 10% and 15% in the population.

Scenario	N Stage 1	N Stage 2	N Enriched	N Total	≥N to Reject Stage 1	≥N to Reject Stage 2	Power All-comers	Power Biomarker+	Power Combined
10% Biomarker +	20	10	20	50	3	6	0.92	0.07	0.98
15% Biomarker +	20	10	20	50	3	6	0.91	0.07	0.98

The proportion of trials that are stopped for futility in this simulation, with or without enrichment, is presented below:

Scenario	Stage 1 Futility No Enrichment	Stage 2 Futility No Enrichment	Enrichment Futility
10% Biomarker +	0.00	0.00	0.01
15% Biomarker +	0.00	0.01	0.01

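### Without enrichment, the pre-specified gene list gets two separate PSA50 rates and no direct contrast; adding one costs nothing and is more sensitive, though still underpowered with 5 to 8 expected carriers

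*Combined protocol and SAP*

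**What the plan says.** Protocol section 10.1.2.1 (under the analysis of exploratory endpoints) and synopsis Statistical Methods (e) i classify each man as biomarker positive or negative on the pre-specified list. They then state: "For biomarker positive and biomarker negative subjects, we will calculate response rates with confidence intervals for hypothesis generation". The calculation is done separately for each testing modality (tissue and cell-free DNA). Section 10.1.2.1 labels it exploratory if only an unselected population is accrued. No between-group measure is named.

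Three other places bear on this:

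- Section 1.3.2 says that the trial will "explore associations between responses with genetic mutations and expression profiles".
- Section 10 says of a trial that passes both stages: "The trial proceeds to complete accrual of 50 subjects in order to better estimate PSA response rate and strengthen data for correlative studies".
- Section 10.1.2.4 analyses the PARP-1 and γH2AX stains against response "using descriptive statistics and Fisher's Exact Tests".

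The objectives in section 2.3 are worded as estimating the PSA50 rate in biomarker-positive patients and, separately, in biomarker-negative patients. Section 10.1.2.2 plans a data-driven search for mutation groupings linked to response, using descriptive analyses and random forests.

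**The concern.** The gene list defines the enrichment cohort and is the only DNA marker fixed in advance. When the trial stays unselected, carriers and non-carriers are enrolled side by side and can be compared directly. With one rate and one interval per group, a reader who wants to know whether mutation status goes with response must compare two intervals by eye, one of them from a handful of men. That is a very conservative comparison: two 95% intervals can overlap when the difference is clear. If a contrast is instead chosen after the data are seen, the modality (tissue or cell-free DNA) and the method are open choices.

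What is at stake is how well an exploratory question is answered. No primary or secondary result, sample size or stopping rule depends on it.

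**Working it through.** **Inputs from the protocol**

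- Stage rules (section 10): "However, if ≥ 3 subjects among the first 20 respond", ten more are accrued; then "If ≥ 6 subjects respond out of 30 in the unselected population after the second stage", the null is rejected and accrual continues to 50.
- Design alternative (section 10.2.2): PSA50 rate 0.30 in all-comers and 0.60 in carriers, with "prevalence of biomarker positive subjects of 10% and 15% in the population".
- Sensitivity range: section 1.3.1 expects 19–23% prevalence in tumor tissue; 20% and 23% are used here.

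**Assumptions**

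- Subgroup intervals are exact (Clopper-Pearson) 95%. The level is not stated for the subgroups; it is borrowed from the primary endpoint in section 10.1.1.
- The contrast is tested at two-sided 0.05. The plan gives no alpha for it.
- Two intervals "show" a difference when they do not overlap. The plan states no rule, so this is only a benchmark.

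**Step 1. Reproduce the plan's figure.** The chance of reaching 50 unselected men is the sum over k = 3 to 20 of P(X₁ = k) × P(X₂ ≥ 6 − k), with X₁ ~ Bin(20, p) and X₂ ~ Bin(10, p).

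- At p = 0.30 this is 0.913 (protocol: 0.92 and 0.91 at the two prevalences).
- At p = 0.10 it is 0.069 (protocol: 0.07).

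So under the alternative about 91% of trials end on this path.

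**Step 2. Non-carrier rate and carrier count.** The non-carrier rate is (0.30 − 0.60 × prevalence) / (1 − prevalence).

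- 10%: 0.24 / 0.90 = 0.267; expected carriers 50 × 0.10 = 5.
- 15%: 0.21 / 0.85 = 0.247; expected carriers 50 × 0.15 = 7.5.
- 20%: 0.18 / 0.80 = 0.225; expected carriers 10.
- 23%: 0.162 / 0.77 = 0.210; expected carriers 11.5.

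**Step 3. Compare the two readings.** Take carriers ~ Bin(50, prevalence) and independent binomial responders in each group. Sum the probability of every table in which (a) the two intervals do not overlap, or (b) Fisher's p ≤ 0.05.

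| Prevalence | (a) Intervals separate | (b) Fisher p ≤ 0.05 |
|---|---|---|
| 10% | 6% | 27% |
| 15% | 13% | 42% |
| 20% | 22% | 56% |
| 23% | 28% | 65% |

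Simulation restricted to trials that pass both stage thresholds gives nearly the same: 6.5% and 13.5% for (a), and 27% and 42% for (b), at 10% and 15%.

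**Step 4. No true difference (0.30 in both groups).** The intervals separate in 0.1–0.2% of trials and Fisher rejects in 2–3%. Comparing by eye is thus far stricter than a 5% test, and Fisher stays below its nominal level.

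**Step 5. Single tables, N = 50**

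| Carriers | Non-carriers | Exact 95% intervals | Fisher p |
|---|---|---|---|
| 5/7 | 10/43 | 29–96% and 12–39% (overlap) | 0.020 |
| 5/8 | 10/42 | 24–91% and 12–39% (overlap) | 0.043 |
| 4/7 | 11/43 | 18–90% and 14–41% (overlap) | 0.18 |
| 3/5 | 12/45 | 15–95% and 15–42% (overlap) | 0.15 |

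The first two rows show what overlap can hide. The last two, close to what the alternative predicts, show that Fisher's test often fails as well.

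**Step 6. What limits power.** By the normal approximation, 80% power would need about 16 to 19 carriers at the design's group ratios, against 5 to 8 expected.

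**Step 7. Other effect sizes, 10–15% prevalence, given the path**

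| Overall / carriers | Intervals separate | Fisher |
|---|---|---|
| 0.30 / 0.50 | 3–5% | 14–22% |
| 0.20 / 0.60 | 22–43% | 55–77% |
| 0.25 / 0.80 | 42–73% | 75–93% |

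**The case against.** The planned analysis matches its written objective, which is to estimate each rate. Fisher's test appears where the objective is worded as association (the protein stains, scored 0 to 3), and the RNA signature, also a binary marker, likewise gets two rates and no test. Section 10.1.2.2 covers mutation–response association in part. Both rates will be reported, so anyone can rebuild the 2×2 table. The gene list ends in an open category of other DNA repair genes, so a p-value may lend rigour to a group that is not closed. The analysis is labelled exploratory, and section 10.3.1 bars subanalyses from supporting efficacy conclusions.

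Most of this stands, and it limits the point to a refinement. It does not remove it. Section 1.3.2 does announce an interest in association with mutations, and the random-forest search is discovery, not a contrast on the fixed list. A contrast rebuilt afterwards has no pre-specified modality or method.

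A reader might infer something stronger: that the missing contrast is the reason the trial would fail to show a real mutation effect. The documents do not support that. With Fisher's test added, the chance at the design prevalence is still only 27–42%; the main constraint is the number of carriers. Nor are the 6–13% figures operating characteristics of the plan, since it never makes interval overlap a decision rule. With a very large effect, separate intervals can suffice (73% at 15% prevalence with 0.80 in carriers and 0.25 overall).

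**Conclusion.** The point holds as a low-severity gap in an exploratory analysis. On the path without enrichment, no direct contrast is named for the pre-specified list. At the design alternative with 50 men, a Fisher contrast would pick up the difference about three to four times as often as non-overlapping intervals at 10–15% prevalence (27/6 ≈ 4; 42/13 ≈ 3), and a little over twice as often at 20–23% (56/22 ≈ 2.5; 65/28 ≈ 2.3). Detection becomes more likely than not only at about 20–23% prevalence or with a wider gap in rates.

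These figures rest on assumed exact 95% subgroup intervals, a two-sided 0.05 test, non-overlap as the benchmark, and all 50 men classified. They do not show an error in the primary design, and the contrast would not make the carrier question well powered.

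**What to change.** In section 10.1.2.1 and synopsis (e) i, for the path without enrichment, add an exploratory analysis of the tissue-based list:

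- the difference in PSA50 rate, carriers minus non-carriers, with an exact or score 95% confidence interval (name which);
- Fisher's exact test as a secondary descriptor, as in section 10.1.2.4;
- the two separate rates kept, with their interval level and method stated;
- a sentence giving the expected number of carriers (about 5 to 8 of 50 at the design prevalence) and the resulting low power, so that a non-significant result is not read as no association.

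Fixing before analysis which genes count under the open category would make the contrast easier to interpret. The cost is a few sentences of text and a line or two of code. No patients, samples or data are added, and the primary test and stage rules are untouched.
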